4.3 Follow Up

Patients will be called 7 days after their visit to the emergency department by a research associate. If they cannot be contacted on that day, they will be contacted the next day (until they are reached, up to one week), and asked to answer the same questions but based off of how they felt 7 days after their visit. This will take place whether or not the patient is admitted or discharged.

4.3.1 7 days after visit to emergency department

- Any new adverse events (yes or no and if yes, list them)
- Record and report any serious adverse event that has been reported by participant
- Medication preference (If the patient were to come back for the same complaint, would they want the same drug? Yes, no or unsure)
- Missed diagnosis (if they present to another emergency department and receive a diagnosis different than what they were discharged with)

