4.4 Missed Measurements

- In the event one of the numerical secondary outcomes is missed, an average of the measurements before and after will be used as a substitute. Any other data point will not be substituted and recorded as missed. These, in addition to allowing up to a 15 minute delay in measuring a variable, will not be counted as protocol deviations.

- If a patient leaves the emergency department prior to 180 minutes, they will no longer be followed for timed measurements. They will still be contacted for the follow up portion of the study.

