4.6 Subject Completion/Withdrawal

Subjects may withdraw from the study at any time without prejudice to their care. They may also be discontinued from the study at the discretion of the Investigator if it is later discovered that they have any exclusion criteria, as determined by chart review or “Care Everywhere”. If the Investigator becomes aware of any serious, related adverse events after the subject completes or withdraws from the study, they will be recorded in the source documents and on the CRF and reported to the IRB.

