5 STUDY EVALUATIONS AND MEASUREMENTS

5.1 Screening and Monitoring Evaluations and Measurements

5.1.1 Medical Record Review

Include a listing of the variables that will be abstracted from the medical chart (paper or electronic).

- Date of birth
- Biologic sex
- Height (inches)
- Weight (kilograms)
- Medical history (diabetes, hypertension, high cholesterol, coronary artery disease, heart failure)

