6.2.4 Safety Analysis

All subjects entered into the study will be included in the safety analysis, with the exception of those who wish to withdraw from the study. The frequencies of AEs by type will be summarized. Serious adverse events will be described in detail. Incidence of all safety outcomes will be summarized along with the corresponding exact binomial 95% two-sided confidence intervals.

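### After the ED assessments end, the only scheduled check for serious adverse events is the patient's own report by telephone, and the plan does not say how patients with no day-7 answer enter the SAE rate

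*Combined protocol and SAP*

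**What the plan says.** Section 4.2 asks for a yes/no SAE entry at each of seven times from 15 to 180 minutes. Section 4.4 ends these entries early for anyone who leaves before 180 minutes, but adds: "They will still be contacted for the follow up portion of the study".

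The follow-up in section 4.3 is a call by a research associate 7 days after the visit. If the patient does not answer, "they will be contacted the next day (until they are reached, up to one week"). On admitted patients the section says: "This will take place whether or not the patient is admitted or discharged". The SAE item for the call (4.3.1) is: "Record and report any serious adverse event that has been reported by participant".

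Two sections mention the medical record. Section 5.1.1 opens with "Include a listing of the variables that will be abstracted from the medical chart" and then lists date of birth, sex, height, weight and medical history, with no outcomes. Section 4.6 says of patients already enrolled: "They may also be discontinued from the study at the discretion of the Investigator if it is later discovered that they have any exclusion criteria", and names chart review and Care Everywhere as the means. Section 4.6 also has the investigator record and report serious events that come to notice after completion or withdrawal, provided they are related.

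For the analysis, section 6.2.4 says "All subjects entered into the study will be included in the safety analysis", except those who wish to withdraw, and asks for exact binomial 95% intervals. For missing items other than numerical secondary outcomes, section 4.4 says: "Any other data point will not be substituted and recorded as missed".

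**The concern.** The SAE definition in section 8.4 includes death and inpatient hospitalization and has no causality condition. A patient who died cannot report, and one who is gravely ill may not. The one scheduled source after the ED is therefore weakest for the events that matter most. The clause in 4.6 is passive and limited to related events, so it does not replace a search.

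The second gap is the denominator. An unreached patient may carry up to seven negative ED entries and no day-7 answer. Section 6.2.4 keeps that patient in the safety analysis and section 4.4 marks the day-7 item as missed. The plan does not say which of these governs a patient-level SAE proportion.

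Three things rest on this count: the SAE incidence with its exact interval (6.2.4), the chi-square comparison of SAEs (6.2) and, as far as it includes post-ED events, the interim safety boundary (6.4). Section 2 aims to show an equal safety profile. Missed events lower the observed rates and, if the share missed is similar in both arms, shrink the absolute difference. That favours a finding of equality.

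**Working it through.** **Inputs from the documents.** Section 6.3 gives alpha 0.05, power 80%, SD 3 and a difference of 1.3. A two-sided t-test then needs 84.57 per arm, rounded up to the stated 85. The total is 2 × 85 × 1.10 = 187, as stated, so an arm has about 94 patients (187/2, rounded up). The 10% loss is a sample-size allowance and not a day-7 contact rate. The documents give neither a contact rate nor an SAE rate.

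**Assumptions.** The unreached share u is 10%, 20% or 30% (about 19, 37 or 56 of 187). The true post-ED SAE risk is 5%. The unreached have either the same risk as those reached or twice that risk. No event in an unreached patient is found. SAEs seen during the timed ED assessments are unaffected.

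**Effect on the rate.** At equal risk with all patients in the denominator, the reported rate is 5% × (1 − u). At twofold risk, let r be the risk in those reached. Then r(1 − u) + 2ru = r(1 + u) = 5%, so r = 5%/(1 + u). The share of events missed is 2u/(1 + u), and the reported rate over all patients is 5% × (1 − u)/(1 + u). Over reached patients only, it is r.

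| u | Equal risk, all | Twofold risk, share missed | Twofold risk, all | Twofold risk, reached only |
|---|---|---|---|---|
| 10% | 4.5% | 18% | 4.1% | 4.5% |
| 20% | 4.0% | 33% | 3.3% | 4.2% |
| 30% | 3.5% | 46% | 2.7% | 3.8% |

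The last column shows that a corrected denominator alone does not remove the bias when the unreached are at higher risk. A second source is needed as well.

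**Effect on the interval.** With zero events the exact upper 95% limit is 1 − 0.025^(1/n). It is 3.85% for n = 94, 4.25% for 85 (9 unreached), 4.80% for 75 (19 unreached) and 5.44% for 66 (28 unreached). At the other extreme, if all 9 unreached patients had an SAE, the rate would be 9/94 = 9.6% (exact interval 4.5% to 17.4%).

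**Effect on the interim rule.** Section 6.4 looks after 94 patients, taken here as 47 per arm, with a boundary of P ≤ 0.025. For x against 0 events, the uncorrected chi-square is 94x²/[x(94 − x)].

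- x = 5: 94 × 25/(5 × 89) = 5.28, P = 0.0216, boundary crossed.
- x = 4: 94 × 16/(4 × 90) = 4.18, P = 0.041, not crossed.

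With a continuity correction, which the plan neither specifies nor rules out, the change falls between 7 against 0 (P = 0.0184) and 6 against 0 (P = 0.0349). Either way, one undetected SAE can change the result.

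**The case against.** The strongest reply is that the plan is less bare than it looks, and several stronger readings do fail.

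- A reader might infer that unreached patients are scored as event-free. No section says so, and 4.4 says that such an item is recorded as missed. The defect is an unstated rule. Scoring them as negative is one way an analyst could fill the gap.
- A reader might infer that every patient stays in the safety denominator. Section 6.2.4 excludes those who wish to withdraw.
- A reader might infer that the call is the only route by which an SAE can become known. Section 4.6 has a passive route for related events, 5.2 lists examinations and routine laboratory data, and 8.1 refers to monitoring throughout the study. None of these schedules a check after the ED, so the call is the only scheduled one.
- A reader might infer that readmitted patients are lost. They are called whether admitted or discharged, the calls are repeated for up to a week, and most could report an admission. The clear failures are death and prolonged incapacity.
- A reader might infer that the IRB reporting times in 8.5 are defeated. That section does not say whether they run from occurrence or from awareness. What stands is that an event never found is never reported, although 8.5 also covers unrelated internal SAEs.

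The size also rests on assumptions. The comparable earlier trial described in 1.2.2.2 had no SAEs, and with zero events and 10% unreached the upper limit moves only from 3.85% to 4.25%. Finally, the content of Table 1 was not in the text available for this check, and 9.4.1 places the DSMB procedure in the IND application. If either names a record check, what remains is to cite it in 4.3.1 and state the denominator.

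**Conclusion.** The point holds in two parts. In the protocol text, scheduled SAE detection after the ED depends wholly on the participant's own report, with no active second source. The plan also leaves open how patients without a day-7 answer enter the SAE numerator and denominator.

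The size cannot be fixed from the documents. Under the stated assumptions, a 5% post-ED risk would be reported as 2.7% to 4.5% if unreached patients are counted with no event. If events are rare and few patients are unreached, the effect on the interval is small. The interim comparison is more fragile, because one event can decide it. This is a design weakness that should be repaired. It is not evidence that the trial's safety result would be wrong.

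**What to change.** - **4.3.1:** for every dosed patient who has not withdrawn, reached or not, the research associate checks the hospital record and Care Everywhere once the call window has closed. The check covers death, admission, ED return and other SAEs occurring from dosing through day 7. Limiting it to patients who have not withdrawn keeps it consistent with 4.6.1 and 6.2.4.
- **5.1.1:** add these outcomes to the abstraction list.
- **6.2.4:** report post-ED SAE incidence over the number ascertained by call or record, show those with neither by arm, and add a sensitivity analysis for unknown status. The range from no events to events in all unknowns would serve.

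The cost is a brief look-up for up to 187 patients by existing staff, in a system the protocol already names. The consent and authorization wording should be checked to confirm that it covers an outcome search. The reported SAE rate may rise slightly, and events at hospitals outside the linked records will still be missed.

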2 STUDY OBJECTIVES

The overall objective of this study is to determine if intravenous lidocaine can have equal analgesic efficacy as hydromorphone while having an equal safety profile in patients with acute abdominal pain.

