2.2 Secondary Objectives (or Aim)

The secondary objectives are to:

- Measure improvement in pain at 15 minutes, 30 minutes, 60 minutes, 120 minutes, 150 minutes and 180 minutes following administration of study drug.
- Measure frequency of sufficient pain relief, defined as no need for pain medication outside of investigational drug.
- Measure the safety of lidocaine, as determined by comparing its rate of side effects, frequency of medication administration required to treat side effects, the frequency of serious adverse events, disposition change attributed to study drug, and frequency of missed diagnosis to hydromorphone.
- To measure patient preference for the study drug they received (would they want it again).

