3 INVESTIGATIONAL PLAN

3.1 General Schema of Study Design

Patients presenting to the emergency department with abdominal pain will be screened for eligibility. Once deemed eligible, they will be randomized to receive either intravenous lidocaine or hydromorphone. The patient, ED nurse and physician will all be blinded to the study drug. Only the research pharmacist will know the drug that the patient is receiving. Primary and secondary endpoints will be measured from the time just before the patient receives the study drug and for the next 180 minutes then once again 7 days later (please refer to Table 1 for timing and specific data being measured). The two drugs will then be compared against one another.

Much of each patient's care will be "standard of care", most likely to include intravenous access, venipuncture, labs, imaging, and potentially consultations by other services. Please refer to Figure 1 for an illustration of study interventions. Standard care can take place at anytime on Figure 1.

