3.3.2 Total Number of Study Sites/Total Number of Subjects Projected

The study will only be conducted in the Hennepin County Medical Center Emergency Department. Recruitment will stop after 187 patients have been consented.

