3.5 Inclusion and Exclusion Criteria

3.5.1 Inclusion Criteria

- 1) Adults at least 18 years of age but no more than 64
- 2) Abdominal (abdomen or flank) pain severe enough to warrant intravenous narcotics (as determined by the clinical team), for a duration of 7 days or less

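### Read literally, the definition of missed diagnosis leaves out returns to the study's own emergency department, so one secondary safety outcome is incompletely captured

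*Combined protocol and SAP*

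**What the plan says.** Section 4.3.1 of the protocol lists what the research associate asks by telephone at day 7. One item defines the outcome: "Missed diagnosis (if they present to another emergency department and receive a diagnosis different than what they were discharged with". No other definition appears in the available text.

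The outcome has a formal role. Section 2.2 closes its list of safety comparisons with "disposition change attributed to study drug, and frequency of missed diagnosis to hydromorphone", and section 6.2 includes it among the proportions compared between arms by chi-square at alpha 0.05. The overall objective in section 2 is equal efficacy "while having an equal safety profile in patients with acute abdominal pain".

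Section 3.3.2 fixes the setting: "The study will only be conducted in the Hennepin County Medical Center Emergency Department". That department is therefore the index department for every patient.

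For the data collected, section 3.1 tells the reader "please refer to Table 1 for timing and specific data being measured". Only the headings of Table 1 survive in the available text, and the call form is not included. Their absence is not a fault in the plan, but it means that the parenthesis in 4.3.1 is all there is to work from.

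**The concern.** A discharged patient whose abdominal pain turns out to have another cause may go back to the department that first saw them. In this trial that is the study's own department. The word *another* in the definition, taken at face value, leaves that patient out and counts the same patient if they go elsewhere. Whether a changed diagnosis is recorded would then depend on where the patient went, not on whether the first diagnosis was wrong.

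At stake is the completeness of one secondary safety comparison. Uncounted events lower the recorded proportion in the arm where they occur and reduce the number of events available to the chi-square test. The wording could also be taken loosely, as any further emergency visit. If callers differ in how they take it, recording will be inconsistent.

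**Working it through.** **1. Does any other section bring own-site returns in?**
- Section 4.3.1 asks separately for adverse events: "Any new adverse events (yes or no and if yes, list them". A return to the study department might be recorded there, or as a serious adverse event under 8.4 if the patient is admitted. Neither record enters the missed-diagnosis proportion.
- Section 5.1.1, the chart abstraction list, covers date of birth, sex, height, weight and medical history. It has no return visits or later diagnoses.
- Section 4.6 mentions chart review, but for finding exclusion criteria after enrolment.
- Sections 2.2 and 6.2 name the outcome without defining it.

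So nothing in the available text repairs the definition.

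**2. Is the plan's sample size involved?** Section 6.3 uses a difference of 1.3, SD 3, alpha 0.05 and 80% power, all for the primary pain endpoint.
- Normal approximation: n = 2 × (1.960 + 0.842)² × 3² / 1.3² ≈ 83.6, so 84 per arm.
- The t-test solution is 84.57, so 85 per arm, as stated.
- 2 × 85 = 170, and 170 × 1.10 = 187, as stated.

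The figure reproduces and contains no missed-diagnosis rate, so rewording the definition does not change it.

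**3. Effect on the comparison.** Let p₁ and p₂ be the true proportions in the two arms, and f the share of true events found only on a return to the study's own department.
- Equal f in both arms: recorded difference = (1 − f)(p₁ − p₂). For f = 0, 0.25, 0.50, 0.75 and 1 the multiplier is 1, 0.75, 0.50, 0.25 and 0.
- The recorded ratio is (1 − f)p₁ / [(1 − f)p₂] = p₁/p₂. It is unchanged for any f below 1.
- Unequal shares f₁ and f₂: recorded difference = (p₁ − p₂) − (f₁p₁ − f₂p₂). The error can then go either way.

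The documents supply no p₁, p₂ or f.

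**4. Illustration on assumed rates only.** Take 85 per arm and equal f. Expected events over both arms = 85 × (1 − f)(p₁ + p₂). Power is for a two-sided two-proportion comparison at 0.05 (normal approximation, pooled variance under the null), using proportions multiplied by (1 − f).

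| f | 2% v 6%: events, power | 5% v 10%: events, power | 5% v 15%: events, power |
|---|---|---|---|
| 0 | 6.80, 26.4% | 12.75, 23.4% | 17.00, 58.6% |
| 0.25 | 5.10, 20.7% | 9.56, 18.4% | 12.75, 45.8% |
| 0.50 | 3.40, 15.1% | 6.38, 13.5% | 8.50, 32.0% |
| 0.75 | 1.70, 9.6% | 3.19, 8.7% | 4.25, 17.9% |

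At the smallest counts the approximation is rough. The table shows two things: lost events cost power, and power is below 80% at every assumed pair even with full capture. Better wording improves capture but does not make this a well-powered comparison.

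**The case against.** The strongest reply is that this is a short parenthesis in a call list, that *another* may loosely mean a further emergency visit, and that Table 1 or the call form may word the question properly. That is possible and cannot be ruled out. It limits the point to the literal definition in 4.3.1, which is the one a reader of the available text would apply.

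The outcome also carries limited weight. It is absent from the synopsis list of safety evaluations and from section 5.2, and some own-site returns may be recorded as adverse events. Both facts stand and keep the point small.

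Four stronger readings are tempting, and the documents do not support them:
- *The plan itself expects own-site returns.* A reader might infer this from the preference question in the same list: "If the patient were to come back for the same complaint, would they want the same drug". That question is hypothetical. It predicts no return within the week and has no bearing on how missed diagnoses are counted.
- *Unrelated illnesses would be counted.* The parenthesis alone does not tie the new diagnosis to the pain that qualified the patient ("Abdominal (abdomen or flank) pain severe enough to warrant intravenous narcotics", section 3.5.1). But the item is labelled as a missed diagnosis and compares the new diagnosis with the discharge one, which already implies the link. Stating the link is a clarification.
- *The result is pulled toward equal safety.* Only the absolute difference shrinks, and only if the shares lost are equal. The ratio does not move. Reading a non-significant chi-square as equality is a separate problem, which rewording this item would not solve.
- *The size can be read from the weight of one patient.* 1/85 is about 1.2 percentage points, but that holds for any yes/no outcome in an arm of 85. It does not say how many patients are lost.

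**Conclusion.** The point holds in a limited form. On its literal wording, the only available definition leaves out patients who return to the study's own department and are found to have a different cause of the same pain, and no other section in the available text adds them. Capture of a secondary outcome compared by chi-square is therefore incomplete. It does not follow that the outcome fails to measure missed diagnosis at all.

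The size cannot be derived, because the documents give neither a missed-diagnosis rate nor a share of patients returning to the study department. If that share is equal in the two arms, the absolute difference and the event counts fall by the factor (1 − f). Blinding makes equality plausible, but nothing in the documents establishes it. The primary endpoint and the sample size are untouched, as are the stopping rules in section 6.4, which use only the primary outcome and serious adverse events. Severity is minor.

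**What to change.** Reword the item in 4.3.1, and the matching day-7 call question, along these lines: *a missed diagnosis is recorded if, within 7 days of the index visit, the patient returns to any emergency department, including the study's own, and is given a diagnosis different from the index diagnosis for the same abdominal or flank pain.* The closing words about the same pain are the clarification discussed above.

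The cost is a slightly longer question on a call that is already planned. No visit, patient or test is added, and the chi-square comparison in 6.2 stays as it is. One limitation remains: the answer still relies on what the patient reports by telephone.

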4.4 Missed Measurements

- In the event one of the numerical secondary outcomes is missed, an average of the measurements before and after will be used as a substitute. Any other data point will not be substituted and recorded as missed. These, in addition to allowing up to a 15 minute delay in measuring a variable, will not be counted as protocol deviations.

- If a patient leaves the emergency department prior to 180 minutes, they will no longer be followed for timed measurements. They will still be contacted for the follow up portion of the study.

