4.2 Study Intervention

4.2.1 Time Zero

- Pain score (1-10)
- Patient placed on monitor
- Vital signs recorded (heart rate, respiratory rate, systolic blood pressure, diastolic blood pressure, pulse oximetry, source of oxygen)
- Study drug administered by patient's nurse (mixed by research pharmacist and sent to the nurse) over 5 minutes

4.2.2 15 minutes after the study drug was started (not after it finished), up to a 15 minute delay will be tolerated

- Pain score
- Vital Signs (same as above)
- Recording of any new symptoms (classified at this point as adverse events)
- Recording of sufficient pain relief (yes or no)
- Recording of any medications to treat adverse events (yes or no). If yes, document was medication was administered, why, and when.
- Recording on whether or not naloxone has been administered (yes or no)
- Recording of any change in disposition thought to be due to study drug (yes or no)
- Recording of any serious adverse event (yes or no)

4.2.3 30 minutes after the study drug was started (not after it finished), up to a 15 minute delay will be tolerated

- Pain score
- Vital Signs (same as above)
- Recording of any new symptoms (classified at this point as adverse events)
- Recording of sufficient pain relief (yes or no)
- Recording of any medications to treat adverse events (yes or no)
- Recording on whether or not naloxone has been administered (yes or no)
- Recording of change in disposition thought to be due to study drug (yes or no)
- Recording of any serious adverse event (yes or no)

4.2.4 60 minutes after the study drug was started (not after it finished), up to a 15 minute delay will be tolerated

- Pain score
- Vital Signs (same as above)
- Recording of any new symptoms (classified at this point as adverse events)
- Recording of sufficient pain relief (yes or no)
- Recording of any medications to treat adverse events (yes or no)
- Recording on whether or not naloxone has been administered (yes or no)
- Recording of change in disposition thought to be due to study drug (yes or no)
- Recording of any serious adverse event (yes or no)

4.2.5 90 minutes after the study drug was started (not after it finished), up to a 15 minute delay will be tolerated

- Pain score
- Vital Signs (same as above)
- Recording of any new symptoms (classified at this point as adverse events)
- Recording of sufficient pain relief (yes or no)

- Recording of any medications to treat adverse events (yes or no)

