- Recording on whether or not naloxone has been administered (yes or no)
- Recording of change in disposition thought to be due to study drug (yes or no)
- Recording of any serious adverse event (yes or no)

4.2.6 120 minutes after the study drug was started (not after it finished), up to a 15 minute delay will be tolerated

- Pain score
- Vital Signs (same as above)
- Recording of any new symptoms (classified at this point as adverse events)
- Recording of sufficient pain relief (yes or no)
- Recording of any medications to treat adverse events (yes or no)
- Recording on whether or not naloxone has been administered (yes or no)
- Recording of change in disposition thought to be due to study drug (yes or no)
- Recording of any serious adverse event (yes or no)

4.2.7 150 minutes after the study drug was started (not after it finished), up to a 15 minute delay will be tolerated

- Pain score
- Vital Signs (same as above)
- Recording of any new symptoms (classified at this point as adverse events)
- Recording of sufficient pain relief (yes or no)
- Recording of any medications to treat adverse events (yes or no)
- Recording on whether or not naloxone has been administered (yes or no)
- Recording of change in disposition thought to be due to study drug (yes or no)
- Recording of any serious adverse event (yes or no)

4.2.8 180 minutes after the study drug was started (not after it finished), up to a 15 minute delay will be tolerated

- Pain score
- Vital Signs (same as above)
- Recording of any new symptoms (classified as this point as adverse events)
- Recording of sufficient pain relief (yes or no)
- Recording of any medications to treat adverse events (yes or no)
- Recording on whether or not naloxone has been administered (yes or no)
- Recording of change in disposition thought to be due to study drug (yes or no)
- Recording of any serious adverse event (yes or no)

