4.5 Rescue Medication Administration

If at any point the patient expressed inadequate analgesia and the treating provider wants to administer a new pain drug, they will be eligible to do so however that will be marked as “Insufficient pain relief”. The patient can continue with the study unless at any point they wish to withdraw. Rescue medication will be administered at the discretion of the treating physician or advance practice provider. Rescue medication will not be lidocaine and will never be given to a patient more than once in this study.

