6.2 Secondary Endpoints

Secondary endpoints will include the following:

- The mean pain improvement at time 15, 30, 60, 120, 150 and 180 minutes (using same test as primary end point).

- Difference in proportion of patients with adverse events, who experience serious adverse events, require medication to treat adverse events, report insufficient pain relief, require naloxone, have a change in disposition, and a missed diagnosis will be evaluated using a Chi-Square test with an alpha level of 0.05.
- Proportion of patients who prefer to receive the same drug at a future visit will be compared as proportions using a Chi-Square test with an alpha level of 0.05.

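### Filling a missed secondary pain score with the average of its neighbours fixes the 15-minute improvement at half the 30-minute improvement and can carry rescue relief back in time (minor; secondary endpoints only)

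*Combined protocol and SAP*

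**What the plan says.** Section 4.4 (Missed Measurements) provides that for a missed numerical secondary outcome "an average of the measurements before and after will be used as a substitute". It limits this to those outcomes: "Any other data point will not be substituted and recorded as missed".

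Section 6.2 lists the numerical secondary outcomes: "The mean pain improvement at time 15, 30, 60, 120, 150 and 180 minutes". Each is compared between arms with the same t-test as the primary endpoint.

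Sections 4.2.1 to 4.2.8 place pain scores at 0, 15, 30, 60, 90, 120, 150 and 180 minutes. The first is taken before dosing. Section 3.1 confirms this: "Primary and secondary endpoints will be measured from the time just before the patient receives the study drug and for the next 180 minutes". Each later score may be up to 15 minutes late.

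Section 4.5 leaves rescue to the treating provider and keeps rescued patients under observation: "The patient can continue with the study unless at any point they wish to withdraw". Section 4.4 does not say what to do when rescue falls between the two scores being averaged.

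**The concern.** Averaging two neighbours is reasonable when both lie on the same smooth part of the pain curve. That fails in two situations here.

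- **At 15 minutes** one neighbour predates the drug. The filled value then carries no information about how quickly the drug worked between 0 and 30 minutes. It imposes a straight line on each such patient.
- **Around rescue** the later neighbour can include relief from another drug. That relief is then counted at a time when the patient had received only the study drug. Insufficient relief is itself a compared endpoint in section 6.2, so rescue may well differ between arms, and this error with it.

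At stake is the accuracy of the secondary timed comparisons, above all the earliest one.

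**Working it through.** **The plan's own figure.** The substitution rule has no figure attached. The only design figure is the sample size in section 6.3 (SD 3, difference 1.3, two-sided alpha 0.05, power 80%). The normal approximation, 2 x [3 x (1.96 + 0.84)/1.3]^2, gives 83.6 per arm with unrounded quantiles. The t-test version gives 84.57, rounded up to 85. Then 170 x 1.10 = 187. The figure reproduces, and nothing below changes it.

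**Step 1: the fill at 15 minutes.** Let S be the score and I the improvement from time zero. The filled score is (S0 + S30)/2. The filled improvement is S0 - (S0 + S30)/2 = (S0 - S30)/2 = I30/2. This follows from the text alone.

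**Step 2: effect on an arm mean.** If a share m is missed at random, the shift is m x (I30/2 - I15). The documents give no 15- or 30-minute means and no missing rate, so all inputs here are assumptions. With I30 = 4 the fill is 2.0:

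| True I15, as share of I30 | True I15 | Error per filled patient | Arm shift, 5% missed | 10% missed | 20% missed |
|---|---|---|---|---|---|
| 25% | 1.0 | +1.0 | +0.05 | +0.10 | +0.20 |
| 50% (linear) | 2.0 | 0 | 0 | 0 | 0 |
| 75% | 3.0 | -1.0 | -0.05 | -0.10 | -0.20 |
| 100% | 4.0 | -2.0 | -0.10 | -0.20 | -0.40 |

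For a central case, take I(t) proportional to 1 - exp(-t/tau), scaled to 4 at 30 minutes. With tau = 10 minutes the true 15-minute improvement is 3.27, about 3.3. The error is 2.0 - 3.3 = -1.3 per filled patient, and 0.10 x (-1.3) = -0.13 in the arm mean.

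**Step 3: effect on the difference between arms.** With equal missing rates the bias is m x (half the difference in I30 - the true difference in I15). At m = 10%:

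- Both arms reach 4 at 30 minutes, with tau 5 and 20 minutes. The true 15-minute values are 3.81 and 2.72, a difference of 1.09. Among filled patients it is 0. The bias is 0.10 x (0 - 1.09) = -0.11.
- I30 of 3 and 4, both arms at 75% of I30 by 15 minutes. The true difference is 3.0 - 2.25 = 0.75. The bias is 0.10 x (0.5 - 0.75) = -0.025.
- I30 of 3 (100% reached) and 4 (50% reached). The true difference is 2.0 - 3.0 = -1.0. The bias is 0.10 x (0.5 + 1.0) = +0.15.

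In these examples the difference shrinks towards zero, but that is not general. With both arms at 25%, the true difference is 0.25 and the fill gives 0.5, so the bias is +0.025, away from zero.

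**Step 4: rescue.** Suppose the 60-minute score is missed and rescue is given between 60 and 90 minutes. The fill is (I30 + I90)/2. If rescue adds R points to the 90-minute improvement, R/2 is credited to 60 minutes, before rescue was given. The same algebra applies at the other filled times. The documents give no basis for R or for how often this would occur.

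**The case against.** The strongest reply is that the effect is small and rests on assumptions. That stands. The error of -1.3 is per filled patient and must not be set against the plan's 1.3, which is a difference between arm means. The like-for-like quantity is the bias in the between-arm difference, about 0.03 to 0.15 points in size in the three main examples of step 3. The 15-minute tolerance also makes missed scores less likely.

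Post-rescue scores also enter the analysis directly wherever they are observed, because rescued patients continue. Section 4.4 does not create that broader issue. What it adds is moving such scores to times before rescue.

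Four stronger readings are tempting and fail:

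- **That the pre-dose score itself is inserted at 15 minutes**, giving zero improvement. It has half weight; the filled improvement is I30/2.
- **That the 30-minute fill is misplaced**, since its neighbours at 15 and 60 minutes centre on 37.5 minutes. The plan already accepts a score between 30 and 45 minutes: "4.2.3 30 minutes after the study drug was started (not after it finished), up to a 15 minute delay will be tolerated".
- **That the rule yields wrong values at 180 minutes or after early departure.** The last timed score is at 180 minutes, and the day-7 call in section 4.3 collects no pain score. With no later score nothing is filled and the value stays missing, as it would under the fix. The rule's silence here, and on consecutive misses, is a gap in wording.
- **That filled values make the confidence intervals too narrow.** Each fill uses only that patient's own scores, so patients remain independent. Assume SD 3 at 15 and 30 minutes (fills then have SD 1.5), means 3.3 and 2.0, 10% filled and n = 85. The variance is 0.9 x 9 + 0.1 x 2.25 + 0.09 x 1.3^2 = 8.48, and the standard error is sqrt(8.48/85) = 0.316. Observed scores alone give 3/sqrt(76.5) = 0.343. The smaller value correctly describes the sampling variation of the filled mean; the trouble is that this mean can be off target. The harm is bias, not false precision.

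**Conclusion.** The concern holds as a minor point on secondary endpoints. It is certain from the text that a filled 15-minute improvement equals half the 30-minute improvement, and that nothing stops a post-rescue score from being averaged into an earlier time. Whether the results are materially biased is not certain. In the central case the arm mean moves by about -0.13 points; under linear onset it does not move. Sign and size both depend on onset shape and missing rate.

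A reader might infer that the secondary pain results will be wrong, or that any onset difference is erased. The documents support only that they can be biased. An onset difference vanishes only among filled patients, and only if the arms have equal 30-minute improvement. A reader might also fear for the main result, but section 4.4 excludes the 90-minute score from substitution.

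**What to change.** Delete the substitution sentence in section 4.4. State instead that the secondary timed pain scores are analysed as recorded, and that the number observed per arm is reported at each time. A prespecified repeated-measures model using all observed scores is an alternative; sections 6.2 and 6.2.2 would then need matching wording, since they name the t-test. The model has one advantage: analysing only the recorded scores at each time uses a different set of patients each time and can itself be biased if missing a score is related to pain.

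If averaging is kept, make it a sensitivity analysis only, at 60, 120 and 150 minutes, where both neighbours are post-dose and evenly spaced. Restrict it to patients with no rescue between the two neighbouring scores.

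The simplest version costs one sentence in section 4.4 and slightly fewer patients at some secondary time points. No study procedure and no sample size changes.
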